- and at the time of advanced imaging follow-up (3 months post-RT and/or at the time of suspected progression).
- c) QOL/MDASI/MMSE evaluations will be undertaken at baseline, , 6 weeks (end RT), 1 month, 7 month, 13 month, 19 month (+/- 6 weeks) after the end of chemoradiation, typically at the time of standard clinical follow-up and preferably close to the date of imaging if imaging is obtained. Neurocognitive evaluation will be undertaken at baseline, 1 month, 7 months, and 19 months after chemoradiation (+/- 6 weeks).
- d) CBCD to be drawn weekly during radiation, and prior to every cycle of adjuvant chemotherapy, beginning with first cycle as per standard of care. Comprehensive metabolic panel will be drawn at least every 8 weeks, or more frequently at primary oncologist's discretion, as per standard practice.
- e) Clinical gadolinium enhanced MRI brain scans will be obtained as per standard clinical practice approximately every 8 weeks after chemoradiation, or per the treating physician's discretion as per standard practice.
- f) Up to 10 patients will optionally receive MET PET during Wk 4. All patients will receive advanced MRI (see appendix for details) at Wk 4 (between fractions 17-20), and an additional advanced MRI scan will be obtained 3 months (+/- 1 week) after completion of chemoradiation and/or at the time of suspected tumor recurrence.
- g) Patients will be followed for tumor progression and survival for up to 5 years from the end of radiotherapy. Tumor progression and date and cause of death will be documented, if known. Studies available in the clinical setting may also be used for study purpose as indicated under study aims.
- i) Only the first 30 patients total will optionally receive pre-radiotherapy MET PET

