Several approaches are possible, ranging from very ad hoc qualitative analysis to complex voxel level image analysis. Here we describe an empiric approach to assessment of the ability of an image to predict volumes at highest risk of recurrence. The goal is to compare the probability of the imaging defined subvolume recurring with the probability of the rest of the tumor recurring. This comparison must take into account two potential confounding variables. First, these two (absolute) volumes will typically be different for a given patient and thus any analysis regarding location of recurrence must be weighted by volume. Second, the imaging defined volume may receive higher (or lower) dose than the rest of the tumor. One means to do this is to stratify the analysis on dose received. For example, assume we categorize the initial PTV in terms of high-dose and low-dose regions. Then for each region (strata) we could compute the following quantities

- 1) P1=Proportion of the imaging sub-volume overlapping with recurrence volume (rVOI)
- 2) P2=Proportion of the non-imaging sub-volume overlapping with rVOI

Evidence for success of the imaging at goal to 'determine tumor sub-volumes at high risk of recurrence' would be given when P1>P2. Across the population of patients, we could perform a stratified test whether E[P1] > E[P2]. Metrics such as sensitivity and specificity will be used to quantify the spatial predictive ability and will be calculated as proportions of volumes. For example, for sensitivity we will calculate the proportion of the rVOI contained in the imaging subvolume. Predictive values (PPV and NPV) could be calculated in a similar manner.

Summary statistics will also be generated describing the volumes of each of these imaging defined sub-volumes and their overlap.

11.4 Secondary objective: To prospectively compare tumor volumes defined by baseline MET PET with baseline high b-value DW-MRI and perfusion MRI A conformality index⁴² will be calculated that compares the MET-PET defined tumor volume with high b-value DW-MRI and perfusion MRI defined tumor volume. Non-overlapping regions of MET-PET tumor volume and MRI tumor volume as well as the overlapping regions will be calculated for each patient and used to calculate conformality indices. Assuming the endpoint is normally distributed, the 95% confidence interval for the mean has half-width = 1.96*Standard error of the mean.

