11.5 Secondary objective: To assess the ability of post-treatment advanced MRI to distinguish true progression from pseudoprogression

Patients will undergo follow-up advanced MRI (including high b-value MRI) within 1-4 months after completion of chemoradiation. Pseudoprogression is the appearance of progression later determined to be treatment effect, rather than actual progression, and typically occurs within the first 3 months after chemoradiation. True progression status at 12 months will be centrally reviewed by a team of neuro-oncologists, neurosurgeons, neuro-radiologists and radiation oncologists. This gold standard assessment at 12

months will identify patients as 'progressors' or 'non-progressors'. There are several ways to analyze this data. In the first, we will simply assess to what extent the advanced MRI imaging metrics obtained shortly after treatment (1-4 months) can predict the true progression status at 12 months. Because there is little uncertainty surrounding patients who have not progressed at 12 months, the second analysis will only involve apparent 'progressors' at 12 months. The outcome will still be the true (or at least gold standard) assessment of progression status at 12 months and the predictors will again be advanced MRI metrics obtained shortly after treatment. This analysis will directly assess the extent to which the advanced MRI imaging can distinguish 'true' from 'pseudo' progressors. Standard ROC type metrics will be reported, including AUC, sensitivity, specificity as well as negative and positive predictive value for defined thresholds. The key metric from the high b-value MRI and perfusion is the quantity of 'abnormal volume'. Although multiple thresholds will be studied we will consider less than 1 cc abnormal volume on 3 month follow-up high b-value MRI and perfusion to be indicative of pseudoprogression whereas >1 cc abnormal volume will be considered indicative of true progression. While of great clinical interest, the proposed study is not powered to provide definitive answers to these questions and these analyses will be hypothesis generating.

11.6 Secondary objective: To provide descriptive data regarding neuro-cognitive function, health-related quality of life and symptoms related to radiation dose received.

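### Section 11.5 does not keep the advanced MRI out of the 12-month progression verdict it is scored against, so its accuracy estimates may be biased upward

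*Combined protocol and SAP*

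**What the plan says.** Distinguishing progression from pseudoprogression is a listed secondary objective (2.2.4). Section 11.5 sets out the analysis.

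- **Index test:** "Patients will undergo follow-up advanced MRI (including high b-value MRI) within 1-4 months after completion of chemoradiation". The main cut is at 1 cc: "we will consider less than 1 cc abnormal volume on 3 month follow-up high b-value MRI and perfusion to be indicative of pseudoprogression". More than 1 cc is read as true progression.
- **Reference:** "True progression status at 12 months will be centrally reviewed by a team of neuro-oncologists, neurosurgeons, neuro-radiologists and radiation oncologists". The verdict is binary, progressor or non-progressor, and is called the gold standard.
- **Analyses:** one in all patients, and one restricted to apparent progressors at 12 months. "Standard ROC type metrics will be reported, including AUC, sensitivity, specificity", together with predictive values.
- **Status:** "the proposed study is not powered to provide definitive answers to these questions and these analyses will be hypothesis generating".

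Other sections bear on what the panel may see. Footnote f of the study calendar (10.2) says "an additional advanced MRI scan will be obtained 3 months (+/- 1 week) after completion of chemoradiation and/or at the time of suspected tumor recurrence". Footnote g allows clinically available studies to be used for study purposes. Section 8.2 leaves biopsy or repeat resection to the physician's discretion. Section 10.5.4 defines progression by enhancing lesions, T2/FLAIR change, new or non-measurable lesions, clinical deterioration and corticosteroid dose, without high b-value or perfusion volume. Section 11.5 does not refer to it.

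**The concern.** An accuracy study needs a reference verdict reached without the index test. If reviewers can consult the high b-value and perfusion images, or know which side of 1 cc the patient fell, part of the agreement between marker and verdict is built in. This is review or incorporation bias.

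The plan leaves this route open, and there are reasons to think it could be used. The Introduction says the group has already reported perfusion imaging as a biomarker for separating progression from pseudoprogression, so reviewers have grounds to rely on it. The analysis restricted to apparent progressors covers the ambiguous cases, where additional imaging is most likely to sway a call. What is at stake is whether a later trial takes up a marker because of its performance or because it helped to write its own answer key.

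**Working it through.** Section 11.5 gives no expected accuracy, sample size or precision, so there is no figure to reproduce. The check is first textual, then illustrative.

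**Can the index test reach the verdict?**

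1. No section masks the panel, and none lists its inputs or criteria.
2. Section 11.5 places pseudoprogression typically within the first 3 months after chemoradiation, and the index window is 1-4 months. A scan prompted by suspicion in that window can itself be the index scan. A later one is the same modality but not the index measurement.
3. Histology is not obtained uniformly (8.2), so some verdicts will rest on imaging and clinical course.
4. The 10.5.4 definition would exclude advanced MRI volumes, but 11.5 does not invoke it.

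Access is therefore possible. It is not stated to occur.

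**How much could it matter?** All inputs here are assumptions; none comes from the documents.

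- *s*: true sensitivity and specificity of the marker, taken as equal
- *e*: independent error rate of the panel
- *f*: share of verdicts that simply copy the marker
- half the patients are true progressors

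Without copying, apparent sensitivity and specificity are s′ = s(1 − e) + (1 − s)e. Among copied verdicts both equal 1 by construction. The mixture is A = s′ + (1 − s′)f.

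- Useless marker, s = 0.50, e = 0: at f = 0.20, A = 0.50 + 0.50 × 0.20 = 0.60.
- s = 0.70, e = 0: at f = 0.20, A = 0.70 + 0.30 × 0.20 = 0.76.
- s = 0.70, e = 0.10: s′ = 0.63 + 0.03 = 0.66; at f = 0.20, A = 0.66 + 0.34 × 0.20 = 0.728.

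| Share copied, f | s = 0.50, e = 0 | s = 0.70, e = 0 | s = 0.70, e = 0.10 |
|---|---|---|---|
| 0 | 0.50 | 0.70 | 0.66 |
| 10% | 0.55 | 0.73 | 0.694 |
| 20% | 0.60 | 0.76 | 0.728 |
| 30% | 0.65 | 0.79 | 0.762 |
| 50% | 0.75 | 0.85 | 0.83 |

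With 70% true progressors, e = 0 and f = 0.20, sensitivity/specificity become 0.576/0.647 for the useless marker and 0.751/0.778 for the 0.70/0.70 marker.

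Within each column the value rises with f, so copying raises apparent accuracy relative to the same panel without access. It need not exceed the marker's true accuracy. In the last column, A reaches 0.70 only when f = (0.70 − 0.66)/0.34, about 12%.

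**The case against.** A reader might infer that the panel is unmasked and that the accuracy results are inflated. The documents support neither statement. They are silent on masking, with no copying there is no inflation, and panel error can pull the estimate below the truth (0.694 against 0.70 at 10% copied).

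Other points on that side also carry weight:

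- **RANO.** If the panel applied 10.5.4, advanced MRI volumes would not enter the criteria. This narrows the gap to a missing cross-reference and a missing masking statement. It does not close it, because reviewers applying 10.5.4 could still have the advanced images in view.
- **Timing.** If the 12 months are counted from the end of chemoradiation, the index scan precedes the verdict by 8-11 months. That gives time for independent evidence to accrue, but an earlier scan can still be read later.
- **Not every verdict can be swayed.** Section 10.5.4 counts failure to return because of death or deterioration as progression. The trial's null and alternative survival rates (65% and 82% alive at 12 months) imply 18-35% dead by then. If all those verdicts were fixed, 20% copied overall would need 0.20/0.82 = 24% to 0.20/0.65 = 31% of the remainder.
- **Error rates.** A reader might wish to turn the bias into a false-positive rate. Section 11.5 names no significance test or threshold, so no such rate follows from the plan.
- **Section 11.3.** A reader might extend the concern fully to the recurrence volume. The case is weaker there. The hypercellular volume is set by threshold (6.2) and MET uptake by automatic segmentation (Appendix 3). The group's earlier work, described in the Introduction, had a team define the failure volume and assessed overlap on co-registered images. That background does not bind this trial, and 11.3 does not say how or when the recurrence volume is drawn.

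The hypothesis-generating label limits the consequences but does not remove the bias.

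**Conclusion.** The point stands as a gap in safeguards, not as a demonstrated error. Section 11.5 leaves open whether the advanced MRI informs the verdict used to score it, and it fixes neither the panel's data nor its criteria. If the test does inform the verdict, AUC, sensitivity and specificity may be biased upward relative to the same panel without access.

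The size is unknown. The figures of 0.60 for a useless marker and 0.76 for a 0.70/0.70 marker assume that 20% of verdicts copy the marker, that half the patients are progressors and that the panel is otherwise perfect. The effect is confined to secondary imaging objectives; the 12-month overall survival test is not touched. This is a cheap improvement worth making before any verdicts are reached, because independence is hard to recover once calls have been made with the images in view.

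**What to change.** In 11.5, state that:

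1. the panel sets 12-month status from the 10.5.4 criteria (conventional MRI, clinical course, steroid record), plus pathology where available and survival;
2. high b-value, perfusion and MET PET images, their volumes and the 1 cc classification are withheld from the review packet until the call is locked;
3. any case in which a reviewer had already seen the advanced MRI is recorded, and the accuracy analysis is repeated without those cases, or in patients whose status rests on independent evidence (pathology, death, unequivocal progression on conventional MRI).

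Item 3 is needed because panel members who treated the patients may already know the scans, and withholding the packet does not undo that.

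In 11.3, as a minor addition, state that the recurrence volume is contoured on conventional contrast-enhanced MRI before the baseline and mid-treatment sub-volumes are overlaid. This is in line with the group's earlier method.

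The cost is a few sentences of protocol text, a fixed reading order and a record of prior exposure. The same team and scans can be used, and only the research adjudication is affected. The downside is that some equivocal cases are judged with less imaging and may have to be recorded as uncertain; the sensitivity analysis will also rest on fewer patients.

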6.0 RADIATION THERAPY

6.1 Radiation Dose and Fractionation

Radiation therapy will be delivered once daily for a total of 30 fractions, five days per week. If treatment is interrupted due to a non dose-limiting adverse event or any reason other than toxicity, including holidays, weather, transportation, or treatment machine problems, the duration of treatment will be extended accordingly. An initial treatment plan will be designed to simultaneously deliver differing doses per fraction to 2 PTV volumes: 60 Gy to the conventional MRI volume (PTV_Low), which is the volume and dose used in standard practice. An additional simultaneous boost will be delivered to the combination of high b-value diffusion and perfusion abnormality alone (PTV_High, the area assumed to be at highest risk of tumor recurrence).

Patients with a negative postoperative high b-value DW-MRI and perfusion MRI following complete resection will be treated to the post-operative resection cavity and conventional T1 MRI contrast-enhancing region to a total dose of 60 Gy, as per standard of care, and will remain on study to be analyzed with the entire study cohort. A negative high b-value DW-MRI or perfusion MRI will be defined as a combined high b-value DW-MRI and perfusion target volume of 1 cc or less. Radiation dose will be prescribed to ensure that at least 95% of the PTV (D_{95%}) should be covered by 100% of the prescription dose.

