We anticipate enrolling 40 patients eligible to undergo a boost of radiation (>1 cc combined high b-value DW-MRI and perfusion MRI abnormality) at our institution. A similar protocol will be opened at a second center and treat an additional 40 patients in an identical fashion. This approach was chosen over a single multi-institutional trial protocol for logistical and financial reasons. Nevertheless, we expect to jointly analyze the data from all 80 patients following trial completion. Center will be included as a stratification variable in the analyses. Allowing for 10% of these patients to be non-evaluable for the primary endpoint, 40 (80) enrolled patients will provide greater than 80% power to detect an improvement in 12 month OS from 65% (based on historical controls) to 82% (40 patients) or 78% (80 patients). These results are based on an exact 1-sided test at alpha=0.10. Once completed, this trial will determine if the treatment is sufficiently promising to warrant further investigation in a multi-center, randomized trial.

11.2 Secondary objective: To estimate progression-free survival, patterns of failure and response rates in relation to values from historical control patients.

Progression Free Survival is defined as the time from study enrollment till the first of death from any cause or progression. Kaplan-Meier estimates of PFS will be generated for all patients on this trial and according to MGMT/IDH1 status. Additionally we will compare the observed PFS at 6 months and 1 year to published values from historical control patients.

Patterns of failure and response rates - Failures will be classified as central, in-field, marginal or distant, based on previously published criteria. Our hypothesis is that including high b-value diffusion and perfusion MRI in treatment planning will reduce the proportion of central failures within the high-dose radiation region. We will explore whether this appears to be the case by comparing this proportion to prior dose escalation studies based on conventional MRI planning alone.

Response rates - The proportion of complete, partial and any responders will be calculated along with 95% likelihood ratio confidence intervals using RANO criteria. The proportion of any responders will also be compared to published values from historical controls.

11.3 Secondary objective: Assess the ability of pre-therapy and week 3 MET PET scans and advanced MRI to determine sub-volumes at high risk of recurrence.

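### Section 11.5 reads absolute abnormal volume after treatment without the same patient's pre-radiotherapy volume, so its accuracy figures can partly reflect baseline tumour burden

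*Combined protocol and SAP*

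**What the plan says.** Section 11.5 asks whether post-treatment advanced MRI can tell true progression from pseudoprogression. Its key metric is the quantity of abnormal volume on high b-value and perfusion imaging. It considers "less than 1 cc abnormal volume on 3 month follow-up high b-value MRI and perfusion to be indicative of pseudoprogression whereas >1 cc" is taken to indicate true progression. Other thresholds will be studied but are not listed. Neither the metric nor the cut-off refers to the patient's pre-radiotherapy volume.

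The same 1 cc appears at entry. Section 11.1 (sample size) plans for patients "eligible to undergo a boost of radiation (>1 cc combined high b-value DW-MRI and perfusion MRI abnormality"). Section 6.1 treats a scan as negative when it is "defined as a combined high b-value DW-MRI and perfusion target volume of 1 cc or less". Patients with a negative scan after complete resection are not boosted but "will remain on study to be analyzed with the entire study cohort".

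Section 11.5 has two analyses. The first asks how well metrics from 1 to 4 months predict progression status at 12 months. The second is restricted to apparent progressors at 12 months. In both, status comes from central multidisciplinary review, and AUC, sensitivity, specificity and predictive values are reported. The section says that the study is not powered for these questions.

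**The concern.** The purpose of Section 11.5 is to learn what the post-treatment scan contributes. An absolute volume mixes two things: how much abnormality the patient had before radiotherapy, and what happened to it afterwards. Only the second is information from the follow-up scan.

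The mixture matters because the Introduction (Functional MR Imaging) reports, from 35 earlier patients, that larger diffusion-defined and perfusion-defined volumes before treatment went with inferior PFS. A large baseline lesion tends to leave a large residual and also tends to progress. Absolute follow-up volume can therefore look discriminating through baseline prognosis alone. The plan's own RANO definition of progression (Section 10.5.4) is, for enhancing lesions, a change from baseline; Section 11.5 names no comparable metric.

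What is at stake is the hypothesis that this analysis passes on to a later study. An encouraging AUC could be credited to the follow-up scan when the pre-radiotherapy scan would have given much the same answer.

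**Working it through.** The documents give no error rate or power for the 1 cc rule, so there is no stated figure to reproduce. The rule can be applied directly.

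**Inputs from the plan.** Follow-up cut-off 1 cc (Section 11.5). Baseline above 1 cc for boosted patients (Sections 6.1 and 11.1). Baseline otherwise capped only at a contiguous volume below one third of the brain (Section 3.1.6), so values far above 1 cc are allowed. No baseline distribution is given; the distributions below are assumptions.

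**Step 1: unchanged lesion.** Let V0 be the pre-radiotherapy volume, s the fractional shrinkage, and V3 = V0 × (1 − s). With s = 0, V3 = V0 > 1 cc. Every boosted patient with an unchanged lesion is on the true-progression side, provided the follow-up volume is the same combined volume as at baseline.

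**Step 2: shrinkage needed to fall below 1 cc.** This requires s > 1 − 1/V0.

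| Baseline V0 | Shrinkage must exceed |
|---|---|
| 2 cc | 1 − 1/2 = 50% |
| 3 cc | 1 − 1/3 = 67% |
| 5 cc | 1 − 1/5 = 80% |
| 10 cc | 1 − 1/10 = 90% |
| 20 cc | 1 − 1/20 = 95% |

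The effect depends on baseline size. A fall from 10 cc to 2 cc is read as true progression; a fall from 3 cc to 0.75 cc is not.

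**Step 3: how often, under assumed baselines.** Take lognormal baselines with median 3 to 20 cc before truncation and log-SD 1, truncated above 1 cc. The share of boosted patients still above 1 cc is 76–99% after a uniform 50% shrinkage, 45–95% after 75%, and 13–76% after 90%.

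**Step 4: the other direction.** An unboosted patient going from 0.3 to 0.9 cc has tripled (0.9/0.3 = 3) and is read as pseudoprogression.

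**Step 5: can baseline alone produce an AUC?** Simulate a follow-up scan with no information of its own.

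- Baselines: lognormal, median 5 or 10 cc, log-SD 1, truncated above 1 cc.
- Change from baseline: independent of outcome, median shrinkage 50%, log-SD 0.5 to 1.0.
- Outcome: log-odds of progression rise by 0.5 or 1.0 per SD of log baseline volume; about half of patients progress.

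| Quantity | Result across scenarios |
|---|---|
| AUC, absolute follow-up volume | 0.59–0.71 |
| AUC, percent change | 0.50 |
| AUC, pre-radiotherapy volume alone | 0.64–0.74 |
| Sensitivity at 1 cc | 0.82–0.98 |
| Specificity at 1 cc | 0.09–0.30 |

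The absolute volume looks informative although the follow-up scan adds nothing. Percent change and the baseline AUC, placed beside it, show why.

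**The case against.** The best defence is that 1 cc is one operating point of an index test, judged against an independent 12-month review. If it performs badly, low specificity will show it. Residual volume is also a coherent hypothesis: the Introduction says that b=3000 imaging separates solid tumour from oedema and normal brain, and Section 6.1 already treats 1 cc or less as negative. The second analysis addresses the stated question most directly and contains only apparent progressors, so a patient whose lesion shrank and who never appeared to progress is outside it. Section 11.5 speaks of metrics in the plural, so change from baseline is not excluded. It does not say that the follow-up volume is the combined volume used at entry.

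Most of this stands, and it limits the point. A reader might infer that unchanged or shrunken lesions will be scored as progression in the trial's results. The documents do not support that: the 1 cc reading assigns nobody's outcome. Nor do they support replacing absolute volume with percent change, since nothing in them shows that change discriminates better.

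One part remains unanswered. Low specificity would expose a poor cut-off, but it would not expose an AUC carried by baseline volume. Nothing prespecified in Section 11.5 would reveal that.

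**Conclusion.** The point holds as a cheap improvement to a secondary, exploratory analysis. The named key metric ignores the pre-radiotherapy volume, so sensitivity, specificity and AUC can partly reflect baseline burden. This applies mainly to the first, all-patient analysis. In the second, baseline volume still varies, but the Introduction links it to PFS and not to true-versus-pseudo status among apparent progressors.

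The arithmetic on unchanged and shrunken lesions is exact but rests on the same volume being measured at both times, and it concerns boosted patients only. The AUC range of 0.59 to 0.71 shows what is possible under assumed distributions and a baseline-only effect; it is not a forecast for this trial. The 12-month reference standard, PFS and 12-month overall survival are untouched.

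**What to change.** In Section 11.5, keep the absolute volume and the 1 cc cut-off, and prespecify beside them:

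- **Change from the same patient's pre-radiotherapy volume:** percent change, or absolute change where the baseline is 1 cc or less.
- **The AUC of the pre-radiotherapy volume alone,** reported next to the AUCs of the follow-up metrics, so that the added value of the follow-up scan is visible.

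State whether the follow-up volume is the combined diffusion and perfusion volume used at entry. Use the scan actually obtained in the 1 to 4 month window. Section 10.2, footnote f, says "an additional advanced MRI scan will be obtained 3 months" after chemoradiation, but adds that it may be at that time and/or at suspected recurrence, so a 3-month scan is not guaranteed for everyone.

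The cost is some wording and a little more analysis, with no new scans. The downside is that percent change is unstable at small baselines; absolute change covers those at 1 cc or less, but values just above 1 cc still need cautious reading.
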